#### Timing of Visits:

- Screening Visit: 3-35 weeks after stroke onset
- Baseline Visit: 1-21 days after Screening Visit (target value = 7 days), and 4-36 weeks after stroke onset

- First therapy session: 1-10 days post-randomization (target value < 5 days)
- Post-therapy Visit: 1-6 days after the last therapy session (target value = 2 days)
- 30 Day Follow Up Visit: 25-35 days after the last therapy session (target value = 30 days)

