### 5.3.2 Baseline Visit

The Baseline Visit occurs 1-21 days after the screening visit (target value = 7 days), and 4-36 weeks after stroke onset. The study site will call the subject 1-2 days before this visit, reminding him/her of the time and place of the visit. The initial portion of this visit is performed by the Assessment Therapist. The Fugl-Meyer test will be rescored, after which subjects will be scored on the Handedness Inventory, and the Stroke Impact Scale-Hand Domain. The amount of any therapy (OT, PT, SLT) that the subject received since the Screening Visit and any new medications will be documented. Each subject will be asked to sign a behavioral contract.

After final eligibility is determined, the remainder of this visit will be performed by one of the site's certified Treatment Therapist. Subjects will be randomized via WebDCU™ to 6 weeks of (a) in-clinic therapy or (b) home-based telerehabilitation in a 1:1 ratio. The Treatment Therapist will provide the subject with the PACES Scale and OPS. The Treatment Therapist will then explain the details related to the subject's newly assigned rehabilitation therapy. For

subjects randomized to in-clinic therapy, this will include review of the content and design of therapy as well as details regarding the location where therapy will be delivered. For subjects randomized to telerehabilitation, the Treatment Therapist will review of the content of therapy and provide training on use of the telerehabilitation system.

The Treatment Therapist and the subject will then schedule the six weeks of therapy sessions.

Note that the Baseline Visit may be broken up into two separate visits not more than 3 days apart at the judgment of the research team. This is not encouraged but it is recognized that this may be useful for selected patients. If this Visit is broken into two separate visits, this will not change the fact that the first therapy session must be 1-10 days post-randomization.

### 5.3.3 Therapy Weeks 1- 6

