#### Therapy:

During each of the ensuing six weeks, all subjects will receive 6 therapy sessions/week, 3 of which will be supervised and 3 of which will be unsupervised. **Each subject will therefore receive a total of 36 therapy sessions**, consisting of **18 supervised therapy sessions** (Monday/Wednesday/Friday, when possible) **and 18 unsupervised therapy sessions** (Tuesday/Thursday/Saturday, when possible) as part of study participation. Each treatment session will be 80 minutes long, including a brief break. Interruptions in this schedule may be unavoidable in some cases, e.g., due to illness or during a holiday. When a supervised therapy session is missed, the study team will schedule a make-up supervised session for the subject. The goal is to have supervised sessions alternate with unsupervised sessions, but this is not required. Similarly, if a subject cannot perform an unsupervised therapy session on an assigned date, a make-up unsupervised session will be scheduled. The study will allow up to 8 weeks for completion of the 36 therapy sessions.

Subjects will be told that, if at any point during an unsupervised session a concern arises or a question comes up, they should wait until the next supervised session to ask the therapist if at all possible, but if the question is urgent they may call the study site. All such calls will be documented.

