#### **5.3.5 Day 30 Follow Up**

Between 25 and 35 days after the last therapy session (target value = 30 days), the subject will return to the central study site for testing, including testing related to the primary study endpoint. The study site will call the subject 1-2 days before this visit, reminding him/her of the time and place of the visit. All testing during the Day 30 Follow Up Visit will be performed by one of the site's Assessment Therapists, who will remain blinded to treatment assignment. To further protect the blinding of the Assessing Therapist, subjects will be reminded not to discuss with the Assessment Therapist any details of their six weeks of therapy. The assessments to be performed include vital signs, FM Scale, Box & Blocks Test, modified Rankin Scale, and Stroke Impact Scale-Hand Subsection. Additionally, the Assessment Therapist will record adverse events (which includes study-related adverse events, serious adverse events, and interval medical history), document any new medications and will document the amount of any therapy (OT, PT, SLT) that the subject received outside of study procedures

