## **7. CRITERIA FOR PREMATURE STUDY TERMINATION**

### **Subject Removal from Therapy:**

As participation in the "Telerehabilitation in the Home versus Therapy In-Clinic for Patients with Stroke" trial is voluntary, the subject may decline study therapy at any time. In addition, the treating investigator may stop study therapy if there is a safety concern. In either case, the subject will continue to be followed through the 30 Day Follow Up visit, unless informed consent is withdrawn.

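### The primary visit is dated only from the last therapy session, so ITT subjects who stop early are, on the natural reading, scored weeks sooner than completers, and never-starters have no stated date

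*Combined protocol and SAP*

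**What the plan says.** Section 5.3 (Timing of Visits) sets the primary visit as "30 Day Follow Up Visit: 25-35 days after the last therapy session (target value = 30 days". Section 5.3.5 repeats the anchor: "Between 25 and 35 days after the last therapy session (target value = 30 days". The Post-Therapy Visit hangs on the same event: "Post-therapy Visit: 1-6 days after the last therapy session (target value = 2 days".

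For subjects who decline study therapy or are taken off it, Section 7 (Subject Removal from Therapy) says: "In either case, the subject will continue to be followed through the 30 Day Follow Up visit, unless informed consent is withdrawn". Section 8.1 defines the primary ITT population as everyone randomised and uses multiple imputation for missing data.

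Other timing rules bear on the anchor. Therapy starts soon after randomisation: "First therapy session: 1-10 days post-randomization (target value < 5 days". Section 5.3.3 provides make-up sessions and some slack: "The study will allow up to 8 weeks for completion of the 36 therapy sessions". Section 5.3.2 has the sessions planned in advance: "The Treatment Therapist and the subject will then schedule the six weeks of therapy sessions".

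The primary ANCOVA in Section 8 adjusts for days from stroke onset to randomisation, baseline Fugl-Meyer, age and site. It does not adjust for the time from randomisation, or from stroke, to the outcome visit. No section gives a different anchor for early stoppers or never-starters.

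**The concern.** The last therapy session is a post-randomisation event, and for an early stopper it is set by the stopping itself. The plan asks for a primary assessment in these subjects and counts them in the primary analysis, yet its only dating rule brings their assessment forward by weeks. That early Fugl-Meyer would be observed and inside its window, so it would enter the ANCOVA as an ordinary 30-day value.

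Timing can matter here. Subjects enter 4-36 weeks after stroke, Section 2.1 refers to weeks of spontaneous recovery, and the plan both balances randomisation on and adjusts for time since stroke. If more in-clinic subjects stop early, and scores rise with time, the in-clinic mean is pulled down and the comparison moves toward non-inferiority. If more telerehabilitation subjects stop early, the comparison moves the other way and power is lost. An arm difference in stopping is plausible because supervised sessions mean 18 trips to the site in one arm and none in the other, but the documents give no stopping rates.

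**Working it through.** **1. The plan's own figures.** Margin 2.05, SD 4.0, one-sided 0.025 (lower bound of a two-sided 95% interval), true difference 0. The normal formula gives 60 per arm for 80% power and the t-based version 61, against the plan's 62. Power at 62 per arm is 0.81. Enrolment: 124/(1 - 0.20) = 155, as stated. The sample size is not in question.

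**2. Days from randomisation to the primary visit.** Inputs from Sections 5.3 and 5.3.3: first session on day 1-10; primary visit 25-35 days after the last session; six sessions a week, Monday to Saturday. Let *s* be the days from first to last session.

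Earliest = 1 + *s* + 25; latest = 10 + *s* + 35; typical = 5 + *s* + 30.

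| Last session done | *s* | Earliest | Typical | Latest |
|---|---|---|---|---|
| First session only | 0 | 26 | 35 | 45 |
| End of week 1 | 5 | 31 | 40 | 50 |
| End of week 2 | 12 | 38 | 47 | 57 |
| End of week 3 | 19 | 45 | 54 | 64 |
| Full 6-week course | 40 | 66 | 75 | 85 |
| Course stretched to 8 weeks | 55 | 81 | 90 | 100 |
| No session | none | not stated | not stated | not stated |

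A stop at the end of week 2 is scored 40 - 12 = 28 days earlier than a 6-week completer. A stop at any point up to the end of week 3 is scored 21-40 days earlier, or about 3 to 6 weeks.

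**3. Illustration of size.** The documents do not give the inputs for this step, so these are assumptions:
- the part of the gain that depends on time accrues linearly over about 77 days (5 + 42 + 30);
- 25-50% of the assumed in-clinic gain of 6.85 points (Section 8, Non-inferiority margin) is due to time alone;
- in-clinic subjects who stop at 2 weeks exceed telerehabilitation stoppers by 10-20 percentage points.

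If all of the gain were due to time, a 28-day advance would be worth 28 × 6.85/77 = 2.49 points per stopper. At 25% it is 0.62, and at 50% it is 1.25.

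Shift in arm difference = points per stopper × excess share of stoppers. Standard error = 4.0 × √(2/62) = 0.718. False non-inferiority rate = Φ(shift/0.718 - 1.96).

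| Share of gain due to time | Excess stoppers | Shift (points) | % of margin | False non-inferiority rate |
|---|---|---|---|---|
| 25% | 10 points | 0.06 | 3% | 3.1% |
| 25% | 20 points | 0.12 | 6% | 3.7% |
| 50% | 10 points | 0.12 | 6% | 3.7% |
| 50% | 20 points | 0.25 | 12% | 5.3% |
| 100% (ceiling) | 10 points | 0.25 | 12% | 5.3% |
| 100% (ceiling) | 20 points | 0.50 | 24% | 10.3% |

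**4. Opposite direction.** If the excess is in the telerehabilitation arm, power is Φ((2.05 - shift)/0.718 - 1.96). It falls from 0.81 to 0.79 at a shift of 0.06 and to 0.71 at 0.25.

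**The case against.** The text does not say the last session *taken*. Sessions are scheduled at the Baseline Visit, so the anchor could be the last *scheduled* session, which would give every subject a date. That reading is possible but is stated nowhere. Make-up sessions and the 8-week allowance make the anchor move with sessions actually done, and at least five sites could resolve the point differently. A one-sentence rule settles it either way.

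A reader might infer that a never-starter's outcome must be missing and imputed. That does not follow. Section 7 points toward obtaining a visit for subjects who decline therapy; what is lacking is its date.

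A reader might also charge the whole 2.49 points to early scoring and quote error rates of 5.3% and 10.3% for 10- and 20-point imbalances. The documents do not support that. The 6.85 points are the assumed gain after a full course of therapy; a subject who stops at 2 weeks loses mainly therapy not received, and a later visit would not restore it. Those rates are ceilings. The imbalance has no source either: the 20% in the sample-size section is dropout from follow-up data, not stopping of therapy by arm. The plan also discourages stopping through phone screening, a behavioral contract and exclusion criteria. Nor does Section 2.1 say that spontaneous recovery spans all of weeks 4-36; Section 3 calls pilot subjects at 7±6 months chronic.

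The Per-Protocol analysis, which requires at least 15 of 18 supervised sessions within 8 weeks, removes early stoppers. It is a sensitivity check and does not repair the primary ITT estimate.

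The present anchor does hold time since therapy constant. That is a weak reason to keep it for people who stopped. It is fair to add that completers themselves range over 66-100 days.

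**Conclusion.** The concern stands as a timing defect in the primary endpoint for part of the primary population. On the natural reading, a stated rule makes outcome time depend on a post-randomisation event: about day 26-57 for stops up to the end of week 2, against about day 66-100 for completers. For never-starters the date is not stated. Nothing in the primary model corrects this.

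Whether it biases the result depends on stopping differing by arm, and the direction depends on which arm stops more. The size cannot be derived from the documents. The illustrative 0.06-0.25 points (3-12% of the margin) and 3.1-5.3% false non-inferiority rate rest on assumed stopping imbalances, an assumed time-driven share of the gain, and linear accrual. The case for change rests on the unequal and undefined timing and does not depend on those figures. The plan should be changed, because the remedy is cheap.

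**What to change.** Leave the visit rule for completers unchanged. In Sections 5.3 and 7, state that for subjects who stop study therapy early or never start, the 30 Day Follow Up is scheduled 25-35 days after the planned end of therapy. The planned end is 6 weeks after the first session, or 6 weeks after the target first-session date if no session was taken. Repeat or cross-refer to the rule in Section 5.3.5.

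In the analysis section, add a by-arm summary of days from randomisation to the primary Fugl-Meyer in the ITT set. This also shows the spread among completers, which the scheduling rule does not remove.

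The cost is one sentence in each section and one table. Early stoppers must be retained a few weeks longer, with a slightly higher risk of losing them, and they are assessed after a longer time off study therapy, when outside therapy is permitted. The sample size stays at 124, with up to 155 enrolled.

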### 5.3.1 Screening Visit

The Screening Visit occurs 3 weeks to 35 weeks after the date of stroke onset. The study site will call the subject 1-2 days before the Screening Visit, reminding the patient of the time and place of the visit. Prior to signing informed consent, the subject will be given the opportunity to become familiar with the Box & Blocks kit, and will be given the option to test him/herself given that only those persons who can score at least 3 blocks in one minute will be potentially eligible.

All procedures at the Screening Visit will be performed by one of the site's certified Assessment Therapists; in selected cases and with prior approval from the overall study PI ([name]), a site may request to have a different member of the research team be trained, certified and approved for performing selected assessments. For a given patient, all assessments should be performed by the same Assessment Therapist, as reasonably possible, across the Screening, Baseline, Post-Therapy, and Day 30 Follow Up Visits.

The study will be explained to the subject, after which the subject will be asked to sign informed consent. Next, screening for eligibility will ensue, including medical history, Fugl-Meyer test, Visual Acuity, Box & Blocks test, Montreal Cognitive Assessment, the 3 rehabilitation exercise test examples (used to insure that the subject is able to successfully follow instructions), and the Geriatric Depression Scale (GDS). Other measurements at this visit will include the modified Ashworth Spasticity Scale of the wrist, the Nottingham Sensory Scale, blood pressure, weight, the modified Rankin Scale, the NIH Stroke Scale, and the Stroke Knowledge Exam. The amount of any therapy (OT, PT, SLT) that the subject received since the time of stroke onset and prior and concomitant medications will be documented. Note that the Screening Visit assessments, with the exception of the Fugl-Meyer test, may be completed thereafter up to and including at the Baseline Visit. This is not encouraged but it is recognized that this may be useful for selected patients.

Subjects deemed eligible at the end of Screening Visit will be given the time and date of the Baseline Visit.

Subjects who are found not to be eligible at this visit will be invited to return to be re-screened, e.g., in 1 month, provided the window for eligibility will still be open and providing that the basis for non-eligibility is potentially resolvable.

### 5.3.2 Baseline Visit

The Baseline Visit occurs 1-21 days after the screening visit (target value = 7 days), and 4-36 weeks after stroke onset. The study site will call the subject 1-2 days before this visit, reminding him/her of the time and place of the visit. The initial portion of this visit is performed by the Assessment Therapist. The Fugl-Meyer test will be rescored, after which subjects will be scored on the Handedness Inventory, and the Stroke Impact Scale-Hand Domain. The amount of any therapy (OT, PT, SLT) that the subject received since the Screening Visit and any new medications will be documented. Each subject will be asked to sign a behavioral contract.

After final eligibility is determined, the remainder of this visit will be performed by one of the site's certified Treatment Therapist. Subjects will be randomized via WebDCU™ to 6 weeks of (a) in-clinic therapy or (b) home-based telerehabilitation in a 1:1 ratio. The Treatment Therapist will provide the subject with the PACES Scale and OPS. The Treatment Therapist will then explain the details related to the subject's newly assigned rehabilitation therapy. For

subjects randomized to in-clinic therapy, this will include review of the content and design of therapy as well as details regarding the location where therapy will be delivered. For subjects randomized to telerehabilitation, the Treatment Therapist will review of the content of therapy and provide training on use of the telerehabilitation system.

The Treatment Therapist and the subject will then schedule the six weeks of therapy sessions.

Note that the Baseline Visit may be broken up into two separate visits not more than 3 days apart at the judgment of the research team. This is not encouraged but it is recognized that this may be useful for selected patients. If this Visit is broken into two separate visits, this will not change the fact that the first therapy session must be 1-10 days post-randomization.

### 5.3.3 Therapy Weeks 1- 6

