A minimum of 5 clinical sites will participate in this study. Each clinical site will conduct all testing and treatment at a single central site, although each clinical site is encouraged to recruit subjects from their referral hospitals. At the central study site, an Assessment Therapist will perform all study testing, blinded to treatment assignment (the subject by necessity is not blinded), while a Treatment Therapist will provide in-clinic therapy as well as direct home-based telerehabilitation. Potential enrollees may be identified through any of several routes, for example, during the acute stroke admission at the clinical site or a referral hospital, during inpatient rehabilitation at the clinical site or a referral hospital, or through other means of community-based recruitment. Study conduct will be highly standardized, including selecting therapy content, delivering therapy, and testing.

The current study aims to critically evaluate the utility of a telehealth approach to motor therapy and stroke education. Telehealth has enormous potential to address unmet needs in the growing population of stroke survivors.

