#### Assessments:

All subjects will undergo a brief set of assessments during the third supervised therapy session then again every 3 supervised sessions until the end of therapy. These assessments will record adverse events (which includes study-related adverse events, serious adverse events, and interval medical history), ascertain subject compliance with the unsupervised therapy sessions, document any new medications, and document the amount of any therapy (OT, PT, SLT) that the subject received outside of study procedures. At the end of supervised sessions 6 and 12, the subject will be briefly asked about any new interval medical history events. In addition, at the end of supervised session 3 and supervised session 18, the PACES, OPS scale, and Patient Satisfaction Questionnaire will each be completed. These brief assessments will be performed by the subject's Treatment Therapist.

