## **11. KEY PERSONNEL AND FACILITIES**

At the clinical site, an Assessment Therapist will perform study testing of primary and secondary efficacy analyses, blinded to treatment assignment (the subject by necessity is not blinded), while a Treatment Therapist will oversee therapy to subjects in the in-clinic and the telerehabilitation groups. Study conduct will be highly standardized, including selecting therapy content, delivering therapy, and testing.

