### **11.1 Study team members at each clinical site**

#### **Site lead investigator:**

The lead investigator at each site will be responsible for supervising and coordinating study procedures, including monitoring study progress and enrollment, as well as insuring that study conduct conforms to all study policies. Although study-related adverse events and SAEs are deemed highly unlikely, reporting and responding to any such reports will be the responsibility of the lead investigator.

**Two or more Treatment Therapists** (licensed occupational therapists or licensed physical therapists, none of which is also an Assessment Therapist):

The Treatment Therapist will oversee and provide study-related therapy. The intent is to have one therapist at each site provide therapy for all enrollees across both treatment groups, with an additional therapist available as backup; if this is not possible, a secondary priority is that a patient receives all of his/her therapy from a single study Treatment Therapist. The Treatment Therapist will also oversee subject randomization, which occurs after completion of all eligibility and baseline testing, as well as those tests that are scored during the six weeks of therapy.

**Two or more Assessment Therapists** (licensed occupational therapist or licensed physical therapist, none of which is also a Treatment Therapist):

One of these assessment therapists is designated as the primary Assessment Therapist and the other as backup. The intent is to have all study assessments performed by a single Assessment Therapist across all enrollees over time at each site; if this is not possible, a secondary priority is that a patient receives all of his/her assessment from a single study Assessment Therapist. Study procedures are designed to ensure that the Assessment Therapists remain blind to subject treatment assignment. The Assessment Therapist will also oversee informed consent as well as verification that all entry/exclusion criteria are satisfied.

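### Section 5.3.2 lists the baseline PACES and OPS after randomisation while section 11.1 puts randomisation after baseline testing; if 5.3.2 is followed, the covariate in the Aim 3 enjoyment contrast may be post-allocation

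*Combined protocol and SAP*

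**What the plan says.** Section 5.3.2 describes the Baseline Visit as a sequence. The Assessment Therapist repeats the Fugl-Meyer and scores handedness and SIS-Hand, and eligibility is settled. The Treatment Therapist then takes over, with allocation and the questionnaire in adjoining sentences: "home-based telerehabilitation in a 1:1 ratio. The Treatment Therapist will provide the subject with the PACES Scale". OPS is given with PACES. The next sentence begins "The Treatment Therapist will then explain the details related to" the assigned therapy. The section also allows that "the Baseline Visit may be broken up into two separate visits not more than 3 days apart", without saying which part the forms belong to.

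Section 11.1 states the order differently. "The Treatment Therapist will also oversee subject randomization", it says, "which occurs after completion of all eligibility and baseline testing, as well as those tests that are scored during the six weeks of therapy". The tests scored during therapy are identified in section 5.3.3, where after supervised sessions 3 and 18 "the PACES, OPS scale, and Patient Satisfaction Questionnaire will each be completed".

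The schedule in section 5.3 marks PACES, OPS and randomisation in the same Baseline column. Section 11 notes that "the subject by necessity is not blinded".

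Section 8.5 defines activity-inherent motivation as change in PACES from baseline, to week 1 (primary) and week 6 (secondary). It compares that change between arms by ANCOVA, with baseline PACES among the covariates. Baseline OPS is used as a predictor of compliance.

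**The concern.** A baseline covariate protects a randomised comparison because allocation cannot have influenced it. PACES asks how much the subject enjoys the activity, so a subject who has just learned that therapy will be at home or in the clinic may answer differently. If that happens, the recorded baseline carries part of the reaction to allocation, and adjusting for it moves the arm contrast.

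The contrast at stake is the test of hypothesis 1.3.2, that enjoyment with telerehabilitation is at least as high as in the clinic. The week-6 analysis uses the same baseline. A downward shift in the telerehabilitation arm would push the contrast in favour of that hypothesis; an upward shift would push it against. OPS matters less because its planned use is to predict compliance across both groups, not to form an arm contrast. The Fugl-Meyer and SIS-Hand baselines are listed before randomisation and are not touched.

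**Working it through.** **Order of events.** Two readings of section 11.1 are possible.

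- *Baseline testing includes PACES and OPS.* The schedule marks both under Baseline, and the same sentence of 11.1 treats the Treatment Therapist's in-therapy measures, which include both, as tests. On this reading 11.1 requires the forms before randomisation and conflicts with the order listed in 5.3.2.
- *Baseline testing means only the Assessment Therapist's measures.* The synopsis allows this, since it says "an Assessment Therapist will perform all study testing, blinded to treatment assignment". On this reading 11.1 does not address the forms, and the order listed in 5.3.2 is the only guidance.

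Either way, no sentence places the forms unambiguously before allocation.

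**Inputs.** The plan gives no SD, effect size or power for PACES, so there is no figure of its own to reproduce. From the documents: 62 per arm (section 8, set for the Fugl-Meyer endpoint and borrowed here) and two-sided alpha 0.05. Assumed: a shift s in the telerehabilitation arm's recorded baseline, and a slope b of week-1 on baseline PACES, with both scores in SD units so that b is also the correlation.

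**Offset.** Let T = 1 for telerehabilitation, Y0 the undisturbed baseline, B = Y0 + sT the recorded baseline, and τ the total arm effect on week-1 PACES W.

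- W = a + bY0 + τT + e
- Substituting Y0 = B − sT: W = a + bB + (τ − bs)T + e
- For the change score: W − B = a + (b − 1)B + (τ − bs)T + e

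The coefficient on T is τ − bs in both models. The offset is −bs, and using PACES as both the subtracted value and the covariate adds nothing to it.

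**Size at |s| = 0.2.** SE = √(2/62) × √(1 − b²), with √(2/62) = 0.180. The false-positive rate takes τ = 0.

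| b | Bias (SD) | SE (SD) | Bias/SE | Two-sided false-positive rate |
|---|---|---|---|---|
| 0.4 | 0.08 | 0.165 | 0.49 | 7.7% |
| 0.5 | 0.10 | 0.156 | 0.64 | 9.9% |
| 0.6 | 0.12 | 0.144 | 0.84 | 13.3% |

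Simulation with 20,000 trials per setting gave 7.6%, 9.7% and 13.1% for a downward shift. Widening the slope to 0.3 and 0.7 (4,000 trials each) gave about 6% and 20%. Over shifts of 0.1 to 0.3 SD with slopes of 0.4 to 0.6, the bias runs from 0.1 × 0.4 = 0.04 to 0.3 × 0.6 = 0.18 SD.

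**Dependence on persistence.** Suppose a fraction c of the shift lasts to week 1 and there is no other arm effect. Then τ = cs and the coefficient is s(c − b). For s = −0.2, the chance of wrongly favouring telerehabilitation (nominal 2.5%) at b = 0.4, 0.5, 0.6 is:

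- c = 0: coefficient +0.08, +0.10, +0.12; chance 7.0%, 9.4%, 13.0%
- c = b: coefficient 0; chance 2.5%
- c = 1: coefficient −0.12, −0.10, −0.08; chance about 0.4%, 0.5%, 0.6%

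**Upward shift.** At s = +0.2, a total telerehabilitation advantage otherwise detected with 80% power is detected with 64%, 58% and 50% power.

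**Could it be seen afterwards?** A comparison of baseline PACES between arms has SE 0.180. Its power is 8.6%, 20.0% and 38.6% for shifts of 0.1, 0.2 and 0.3 SD.

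**The case against.** The strongest case against is that section 5.3.2 only narrates tasks in successive sentences. Its one sequencing word in that run places the therapy explanation after the forms, and section 11.1, the only explicit timing rule, points to the order one would want. The rows of the schedule even show PACES and OPS above randomisation, though row order proves nothing. This stands to the extent that post-allocation collection is the listed order, not an established fact, and a reader should not infer that every reading of the documents leads to it.

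A second objection also stands: bias requires the subject to know the arm when completing the form. That subjects are unblinded says nothing about when they learn their assignment, and the documents do not say whether it is disclosed or withheld until the forms are done.

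Third, the double use of baseline PACES might suggest a compounded bias. The algebra shows that it does not compound.

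Fourth, the error rates might be read as general. They hold only when the total arm effect on week-1 PACES is zero; if a downward reaction persists fully and nothing else differs, the chance of wrongly favouring telerehabilitation falls below 1%. What survives is the offset of −bs relative to the total arm effect, which does not depend on persistence.

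**Conclusion.** Sections 5.3.2 and 11.1 should be reconciled. Following 5.3.2 as listed could put a post-allocation covariate into the Aim 3 enjoyment contrast at weeks 1 and 6. That bias is possible and not demonstrated: it rests on the forms being completed after randomisation and on the subject knowing the arm, and the documents settle neither.

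The sizes above are illustrations built on an assumed shift and slope, so the 8% to 13% false-positive range should not be quoted as a property of the trial. The point is limited to a secondary outcome. It is worth correcting because the correction is nearly free and a later balance check would usually miss a shift of this size.

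**What to change.** State in section 5.3.2, in line with 11.1, that PACES and OPS are completed before the WebDCU randomisation step, including when the Baseline Visit is split in two. The Treatment Therapist can still administer them. The cost is one sentence and a reordering within an existing visit, with no new staff, visit or measurement.

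Only if some forms were completed after randomisation, add a sensitivity contrast of the week-1 PACES score itself, dropping the baseline PACES term and keeping the other section 8.5 covariates. The outcome must be the score and not the change, because an unadjusted change carries the whole shift (an offset of −s). This contrast is free of the bias but less precise: its SE is 0.180 against 0.156 SD at slope 0.5, about 15% larger. A test of baseline balance should not replace it, given 20% power at a 0.2 SD shift.
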